11.6.3 Liver Function Test Parameters

Liver Function Testing

Liver function testing (ALT, AST, GGT, ALP, direct bilirubin, and total bilirubin) must be performed as noted in [Table 3-2](#) for serum chemistry, while subjects are receiving study drug treatment and at the Safety Follow-up Visit. These blood samples should be processed and shipped immediately per the Laboratory Manual.

Subjects with new treatment-emergent ALT or AST elevations of $>3 \times \text{ULN}$ and clinical symptoms must be followed closely, including repeat confirmatory testing performed by the central laboratory within 48 to 72 hours of the initial finding and subsequent close monitoring of ALT and AST levels, as clinically indicated. In addition, if ALT or AST is $>5 \times \text{ULN}$, repeat follow-up levels must be obtained within 7 ± 2 days.

If a subject cannot return to the site for liver function testing, a local laboratory may be used. Elevations in LFTs at the local laboratory must be reported immediately to the medical monitor, and the subject must have the tests repeated and sent to the central laboratory as soon as possible (ideally within 48 to 72 hours).

Study Drug Interruption

Study drug administration **must be interrupted** immediately (before confirmatory testing), and the medical monitor must be notified, if any of the following criteria is met:

- ALT or AST $>8 \times$ ULN
- ALT or AST $>5 \times$ ULN for more than 2 weeks
- ALT or AST $>3 \times$ ULN, in association with total bilirubin $>2 \times$ ULN and/or clinical jaundice

A thorough investigation of potential causes should be conducted and the subject should be followed closely for clinical progression.

If no convincing alternative etiology (e.g., acetaminophen use, viral hepatitis, or alcohol ingestion) for the elevated transaminases is identified, regardless of whether ALT or AST levels have improved, study drug treatment must be permanently discontinued if repeat testing within 48 to 72 hours confirms the initial elevation. Subjects in whom treatment is discontinued for elevated transaminases should have their transaminases monitored closely until levels normalize or return to baseline.

Resumption of Study Drug

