11.6.5 Electrocardiograms

Standard 12-lead ECGs will be performed using a machine with printout according to the Schedule of Assessments ([Table 3-1](#) and [Table 3-2](#)). Additional standard 12-lead ECGs will

be performed at any other time if clinically indicated. The performance of all ECGs will adhere to the following guidelines:

- The subject will be instructed to rest in the supine position for at least 5 minutes before having an ECG performed.
- The ECG will be performed before any other procedures that may affect heart rate, such as blood draws.

The ECG traces will be manually read at the study site at the Screening Visit and Safety Follow-up Visit. A printout of the ECG traces will be made for safety review by the investigator and maintained with source documentation. Clinically significant ECG abnormalities occurring during the study through the Safety Follow-up Visit will be recorded as AEs.

To ensure safety of the subjects, a qualified individual at the study site will make comparisons to baseline measurements. If the QTcF is increased by >45 msec from the baseline or an absolute QTcF value is ≥ 500 msec for any scheduled ECG, 2 additional ECGs will be performed approximately 2 to 4 minutes apart to confirm the original measurement. If either of the QTcF values from these repeated ECGs remains above the threshold value (>45 msec from baseline or ≥ 500 msec), a single ECG will be repeated at least hourly until QTcF values from 2 successive ECGs fall below the threshold value that triggered the repeat measurement.

If the QTcF value remains above the threshold value (>45 msec from the average of the 3 predose values on Day 1 or ≥ 500 msec) on repeated measurement or is noted on >2 occasions with no identified alternative etiology for the increased QTcF study drug, then discontinuation from study drug treatment may be required after discussion with the medical monitor.

Subjects in whom treatment is discontinued for increased QTc should have their QTc monitored closely until it normalizes or returns to baseline.

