8 STATISTICAL ANALYSIS

8.1 General Considerations

The Schedule of Assessments is provided in [Appendix A \(Section 10.1\)](#).

All individual subject data for those randomized or exposed to study drug will be presented in data listings.

Continuous variables will be summarized using the following descriptive summary statistics: the number of subjects (n), mean, standard deviation (SD), standard error (SE), median, minimum value (min), and maximum value (max).

Categorical variables will be summarized using counts and percentages.

Baseline Value, unless otherwise specified, is defined as the most recent non-missing measurement (scheduled or unscheduled) collected prior to the first dose of study drug. For ECGs, the baseline will be defined as the average of the 3 pretreatment measurements (triplicate) on Day 1.

Absolute Change from baseline will be calculated as Postbaseline value - Baseline value.

Relative change from baseline will be calculated and expressed in percentage as $100\% \times (\text{Postbaseline value} - \text{Baseline value}) / \text{Baseline value}$.

Treatment Emergent (TE) Period will include the time from the first dose to Safety Follow-up Visit. For subjects who do not have a Safety Follow-up Visit because they rolled over into the open-label extension study within 28 days after the last dose of study drug, the end of the TE period will be the date of rollover into the extension study. For subjects who do not have a Safety Follow-up Visit and did not roll over into the extension study, the end of the TE period will be 28 days after the date of last dose. The TE period will be used for safety analyses unless otherwise specified.

Unscheduled Visits: Unscheduled visit measurements will be included in the analysis as follows:

- In scheduled visit windows per specified visit windowing rules;
- In the derivation of baseline and last on-treatment measurements;
- In the derivation of maximum/minimum on-treatment values and maximum/minimum changes from baseline values for safety analyses;
- In individual subject data listings where appropriate.

Visit Windowing Rules: The analysis visit windows for protocol-defined visits are provided in [Appendix B \(Section 10.2\)](#). The windows will be applied using the following rules for both scheduled and unscheduled visits:

1. If no measurement is available within a visit window, the assessment will be considered missing for the visit;

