2. If there is more than one measurement available within the same visit window, use the following rules:

For all efficacy parameters, if there are multiple measurements within a visit window, the record at the scheduled visit will be used. Otherwise,

- If there are no measurements at the scheduled visit, then the record closest to the target day will be used;

- If there are multiple records with the same distance to the target day, the latest record will be used.
- Assessments at early treatment termination (ETT) visit will follow the windowing rules for regular visits up to Week 72.
- Assessments at safety follow-up (SFU) visit will follow the windowing rules for regular visits if it falls within the upper boundary of the window for Week 72, or remain as SFU if it goes beyond the upper boundary of the window for Week 72.

For all safety parameters, if there are multiple measurements within a visit window, then 1) the record closest to the target day will be used; 2) if there are multiple records within the same distance from the target day, the latest record will be used; or 3) SFU visit will not be windowed, instead, used per nominal visit in relevant analyses.

Incomplete/Missing data will not be imputed, unless otherwise specified.

Outliers: No formal statistical analyses will be performed to detect or remedy the presence of statistical outliers, unless otherwise specified.

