8.4.3 Standard 12-Lead Electrocardiogram

For the treatment emergent ECG measurements, a summary of raw values and change from baseline values will be provided by treatment group at each scheduled time point for the following standard 12-lead ECG measurements: PR, QT, and QTc for HR intervals (QTcF), QRS duration, and HR.

The number and percentage of subjects with ECG event meeting threshold criteria during the treatment-emergent period will be summarized by treatment, ECG parameters, and visit. The threshold criteria are provided in [Appendix H \(Section 10.8\)](#).

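### By-visit QTcF summaries keep the last same-day ECG, which the repeat rule drives below the trigger, and SAP 8.4.3 does not say that threshold counts use the maximum

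*SAP*

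**What the plan says.** SAP 8.1 brings unscheduled measurements into the analysis "In scheduled visit windows per specified visit windowing rules", and says of the windows: "The windows will be applied using the following rules for both scheduled and unscheduled visits". When a safety parameter has several records in one window, "the record closest to the target day will be used"; failing that, "if there are multiple records within the same distance from the target day, the latest record will be used". Efficacy parameters are ordered differently: the record from the scheduled visit comes first, and distance to the target day matters only if there is none. SAP Appendix B (Table 10-3) lists the 12-lead ECG among the windowed assessments, with targets and windows in study days.

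Protocol 11.6.5 sets the repeat rule. A scheduled ECG with QTcF more than 45 msec above baseline, or 500 msec or more, leads to two further ECGs a few minutes apart. If either is still above the threshold, "a single ECG will be repeated at least hourly until QTcF values from 2 successive ECGs fall below the threshold value" that set off the repeats.

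SAP 8.4.3 reports raw QTcF and change from baseline at each scheduled time point. Threshold events "during the treatment-emergent period will be summarized by treatment, ECG parameters, and visit". The QTc rows in Table 10-10 are >450 msec (men), >470 msec (women), ≥500 msec, and increases of >10, >20, >40 and >60 msec. For LFTs and CPK, SAP 8.4.2 asks for threshold counts both per visit and over the treatment-emergent (TE) period. SAP 8.1 also admits unscheduled values "In the derivation of maximum/minimum on-treatment values and maximum/minimum changes from baseline values for safety analyses", but 8.4.3 does not invoke that clause.

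**The concern.** The repeat sequence has a stopping rule that depends on the outcome: it ends when QTcF is low enough. The SAP then keeps the last record of the sequence. A subject who never triggers keeps the scheduled value. A subject who triggers has that value replaced by one constrained to lie under the trigger. The replacement goes in one direction only and affects only the subjects who showed the signal. If QTcF prolongation were more frequent on active drug, the by-visit comparison would be pulled towards no difference. Safety is the only secondary objective visible in the documents, and ECGs are one of its named endpoints.

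**Working it through.** The plan gives no figure on this point, so there is none to reproduce. The check traces the two rules together and then illustrates the size with assumed values.

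**1. Same-day repeats tie.** Distance = |study day − target day|. At Week 4 (target day 29), an ECG and its repeats all taken on day 31 each have distance |31 − 29| = 2. The tie rule then selects the latest.

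**2. How a sequence can end.** Either both early repeats are under the threshold, or hourly ECGs continue until two in a row are. In both cases the last record is below the trigger. The exceptions are a QTcF that never falls, repeats that run into another study day, and a subject who meets both triggers when only one clears (see objection).

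**3. One subject, assumed values.** Baseline is 410 msec; same-day ECGs are 505, 498, 470, 452 and 448 msec.
- Record kept: 448, a change of 448 − 410 = +38.
- Scheduled record, which is also the maximum: 505, a change of 505 − 410 = +95.
- Rows lost under the kept record: ≥500, >60 and >40. Rows still met: >20 and >10.
- Effect on the mean change of a 20-subject arm: (95 − 38)/20 = 2.85 msec.
- Effect on a count: 1/20 = 5% of the arm.

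**4. Which rows lose most.** A simulation of 60,000 visits assumed baseline mean 410 msec (SD 15), true increase 35 msec, within-day SD 10 msec, at most 12 hourly repeats, and repeats continued until both triggers cleared. It produced 9,477 triggered visits. Numbers of those visits above each limit:

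| Limit | Scheduled ECG | Latest record | Maximum |
|---|---|---|---|
| ≥500 msec | 86 | 2 | 96 |
| increase >60 msec | 419 | 0 | 577 |
| increase >45 msec (trigger, not a SAP row) | 9,461 | 2 | 9,467 |
| increase >40 msec | 9,474 | 1,715 | 9,476 |
| >450 msec | 7,130 | 3,188 | 7,295 |

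The latest record gives 2/86 = 2.3% of the scheduled-ECG count at ≥500 msec and none at >60 msec. It gives 1,715/9,474 = 18.1% at >40 msec and 3,188/7,130 = 44.7% at >450 msec. The few latest records still above a trigger come from the cap on repeats.

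**5. What the simulation does not show.** It does not estimate how often triggers will occur. With the same within-day SD, the triggered visits out of 60,000 were 0, 381, 9,477 and 29,850 for true increases of 0, 20, 35 and 45 msec. The documents give no basis for choosing among these. The direction was the same in every scenario that produced triggers.

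**The case against.** The strongest reply is that 8.4.3 counts subjects with an event in the TE period and never says the count uses the single windowed record. SAP 8.1 separately admits unscheduled values to maximum changes from baseline for safety analyses. In Appendix H the only thresholds defined as change from baseline are those for ECGs and vital signs, so that clause may well have been meant for these tables. This reading is open, and it makes the loss from the threshold counts conditional. It does not settle the matter: 8.4.3 asks for counts per visit, does not mention maxima, and lacks the explicit TE-period count that 8.4.2 has. Nor does it touch the by-visit means and changes, which do use the windowed record.

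Other points that stand:
- Below the trigger is not the same as normal. A kept value can still exceed 450 or 470 msec, or be 41 to 45 msec above baseline.
- If both triggers are met, the protocol does not say which must clear. With baseline 430, first value 505 and last value 495 msec, the last is under 500 but still +65, so it counts as >60.
- The effect needs the repeats to be in the database; the documents do not show how the CRF handles them.
- The event is not hidden from the trial. Individual data are listed, clinically significant ECG abnormalities become adverse events, and the IDMC reviews safety data. Safety analysis is descriptive only.

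A reader might infer that a QTcF of 500 msec or more could drop out of every threshold row. The documents do not support that, given the lower rows and the open reading of 8.4.3.

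A reader might also extend the point to liver tests, because for the higher elevations "repeat follow-up levels must be obtained within 7 ± 2 days". There, nothing makes the repeat lower than the first value, since testing does not continue until a threshold is cleared. SAP 8.4.2 also already has TE-period counts, plots of maximum values and a full listing for subjects with elevated results. Nor do the documents contain a repeat-until-below rule for vital signs.

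**Conclusion.** The point holds for ECGs. Followed as written, SAP 8.1 selects a QTcF value on an outcome-dependent stopping rule, and nothing in either document exempts ECGs. By-visit QTcF means and changes are biased downward in subjects who triggered. If the by-visit threshold counts use the windowed record, the event is lost from the row it breached: ≥500 msec, and generally >60 msec. Rows for >450/470 and >40 msec may still count it.

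This rests on the repeats being recorded, falling on the same study day and running to completion. It does not apply clearly to the Safety Follow-up Visit, which is used by nominal visit. The overall size cannot be given because the trigger frequency is unknown. With about 20 subjects per arm, one lost event is about 5% of an arm. The case would remain visible in listings and adverse events, so the fault lies in the summary tables, which could disagree with them.

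**What to change.** 1. In SAP 8.1, for by-visit ECG summaries, take the scheduled-visit record first, as is already done for efficacy, and use a repeat only when no scheduled record exists. The scheduled ECG is not chosen on its own value, so the means are not distorted by the repeat rule.
2. In SAP 8.4.3, state that by-visit ECG threshold counts use the worst post-baseline value in the visit window, unscheduled repeats included.
3. In SAP 8.4.3, add a TE-period threshold count based on the maximum value, parallel to the one in 8.4.2 for LFTs.

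The cost is SAP text and a small programming change before database lock, with no new data. Reported QTc counts may be slightly less favourable. The maximum can also count somewhat more events than the scheduled ECG alone, because triggered visits have more ECGs (577 against 419 for >60 msec in the simulation). No change to the clinical repeat rule is implied.

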8.2 Background Characteristics

8.2.1 Subject Disposition

The number of subjects in the following categories will be presented:

- All Subjects Set (randomized or dosed)
- Randomized
- Randomized but not dosed
- Full Analysis Set (FAS)
- Safety Set

The number and percentage (based on Full Analysis Set) of subjects in each of the following disposition categories will be presented:

- Completed study drug treatment
- Treatment ongoing
- Prematurely discontinued treatment and the reason for discontinuations
- Completed study
- Prematurely discontinued the study and the reasons for discontinuations

8.2.2 Subject Demographics and Baseline Characteristics

[figure not shown]
Demographic and baseline characteristics data will be summarized based on the FAS.

Demographic data will include the following:

- Sex (female and male)
- Age
- Age group at screening (<18, and ≥18 years)
- Ethnicity (Hispanic or Latino, not Hispanic or Latino, and not collected per local regulations)
- Race (White, Black or African American, Asian, American Indian or Alaska Native, Native Hawaiian or Other Pacific Islander, and Other)

Baseline characteristics will include the following:

- Weight (kg)
- Height (cm)

Disease characteristics will include the following:

- Percent predicted FEV₁ at baseline
- Sweat Chloride at screening
- Use of dornase alfa
- Use of inhaled antibiotic
- Use of bronchodilator
- Use of inhaled bronchodilator
- Use of inhaled hypertonic saline
- Use of inhaled corticosteroids
- Colonization of *Pseudomonas aeruginosa* (Positive, Negative)

- Brody/CF-CT total score at baseline

8.2.3 Prior and Concomitant Medications

Medications taken during this study will be coded using the World Health Organization Drug Dictionary Enhanced (WHO-DDE) and categorized as the following:

- **Prior medication:** any medication that started before the first dose of study drug, regardless of when the medication ended.
- **Concomitant medication:** medication continued or newly received at or after the first dose of study drug through the end of TE period.

- **Post-treatment medication:** medication continued or newly received after the TE period.

A given medication can be classified as a prior, a concomitant, or a post-treatment medication; both prior and concomitant; both concomitant and post-treatment; or prior, concomitant, and post-treatment. If a medication has a missing or partially missing start/end date and it cannot be determined whether it was taken before the first dose, concomitantly, or beyond the TE period, it will be considered as prior, concomitant, and post-treatment.

For the FAS, prior medications and concomitant medications will be summarized descriptively by: 1) preferred name; and 2) anatomic class (ATC) level 1, ATC level 2, and preferred name. Frequent ($\geq 5\%$ in any treatment group) prior medications and concomitant medications will be summarized descriptively by preferred name. Post-treatment medications will be listed by subject.

Details for imputing missing or partial start and/or stop dates of medication are described in [Appendix C \(Section 10.3\)](#).

8.2.4 Study Drug Exposure

Exposure summaries will be based on the Safety Set.

Duration of study drug exposure is defined as: last dose date – first dose date + 1 day, regardless of any interruption in dosing between the first and the last dose. For the purposes of DMC, if the date from End of Dosing CRF page is not available, the end of treatment date will be assumed to be the date of datacut.

Duration of study drug exposure, as well as number of tablets administered defined as (Total number of tablets dispensed) - (Total number of tablets returned), will be summarized descriptively (number, mean, SD, SE, median, minimum, and maximum). Additionally, the total duration of study drug exposure, defined as the sum of the subject's duration of treatment exposure and expressed in patient years, will be provided.

If the last dose date of study drug is missing, the latest of the date of subject's treatment discontinuation or the date of treatment completion will be used for analysis purposes.

8.2.5 Study Drug Compliance

Study drug compliance will be measured by the compliance rate; summarized based on the Safety Set and presented by treatment group.

Compliance rate will be calculated as follows:

$$100 \times [1 - (\text{Total number of days study drug interrupted}) / (\text{Duration of study drug exposure})].$$

The total number of days study drug interrupted is defined as the total of number of days the study drug was interrupted in each interruption interval; where number of days study drug interrupted in each interval is defined as the interruption end date - the corresponding interruption start date + 1.

The Compliance rate will be summarized descriptively by the number of subjects (n), mean, SD, median, min, and max and into the categories of <80% or ≥80%.

A list of subjects with <80% compliance rate will be provided.

8.2.6 Important Protocol Deviations

Important protocol deviations (IPD) are a subset of protocol deviations that may significantly impact the completeness, accuracy, and/or reliability of the study data or that may significantly affect a subject's rights, safety, or well-being. IPD rules will be developed and finalized before database lock.

The protocol deviations that should be considered as potential IPDs include, but are not limited to:

- Violation of subjects rights, safety or well-being
- Subject entered the study despite violation of any inclusion or exclusion criteria
- Subject was less than 80% compliant with study medications
- Subject received excluded concomitant medications
- Subject received the wrong treatment or incorrect doses
- Subject remained in study despite meeting withdrawal criteria

Occurrence of any of these events should be considered as potential IPDs, but the blinded team should categorize them as IPDs only if they have the potential to affect interpretation of study results.

IPDs (from the clinical database or from the site deviation log) will be summarized descriptively based on the FAS and presented by treatment group. Additionally, IPDs will be provided as a subject data listing.

8.3 Efficacy Analysis

[figure not shown]
Assessment of efficacy of VX-661/ivacaftor is the primary objective of this study.

